374 nurses will also receive an education pack on chlamydia testing. Payments will be made
375 every three months to the participating clinic.
- 376 • Partner notification information and resources will be provided including referral to
377 www.letthemknow.org.au, a partner notification resource for health care providers and
378 patients.

379 The intervention will be in place for up to four rounds of annual chlamydia testing.

380 ***Chlamydia diagnosis and case management***

- 381 • Self-collected specimens will be recommended where possible, including first catch urine
382 specimens from men or women or self-collected vaginal swabs for women. If a female
383 patient is having a Pap smear during her consultation, an endocervical swab can also be
384 used. In Australia, the National Cervical Screening Program promotes routine screening with
385 Pap smears every two years for women between the ages of 18 (or two years after first
386 sexual intercourse, whichever is later) and 69 years [83].
- 387 • Diagnosis will be based on nucleic acid amplification tests (NAAT) conducted through the
388 clinic's usual pathology provider using their own testing and results reporting protocols.

- 389 • First line treatment for uncomplicated chlamydia in Australia is 1 gram Azithromycin as
390 consistent with the National Management Guidelines for Sexually Transmissible Infections
391 [84].
- 392 • Anyone diagnosed positive for chlamydia is recommended to have a test for repeat infection
393 3 months after the initial diagnosis.
- 394 • Partner notification is recommended for all sexual partner in the past 6 months, in line with
395 the Australasian Contact Tracing Manual guidelines [85].

396 ***Control group***

397 Control GP clinics and AMSs will be asked to continue diagnosis and management of chlamydia
398 according to their usual practice and consistent with the Royal Australian College of GPs (RACGP)
399 guidelines for preventive activities ('Red Book') [35]. GPs in the control arm of the trial will receive a
400 minimal education pack with information on the diagnosis of PID and epididymitis and partner
401 notification. This is to ensure that, as much as is possible, diagnosing practices for PID and
402 epididymitis are consistent across the two arms of the trial, and that patients are encouraged to
403 notify sexual partners of a positive chlamydia diagnosis.

404 ***Randomisation sequence generation***

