569 overall numbers of events in intervention and control clinics will be reported. Diagnoses of anxiety
570 and referrals for psychological or psychiatric treatment will be extracted from the clinics' electronic
571 medical records where possible. However, it will not be possible to assess causality from these data.
572 In the final prevalence survey, the questionnaire administered to patients attending both
573 intervention and control clinics will ask them to report whether they experienced any anxiety or
574 issues with their partner following any chlamydia test they had during the intervention period and
575 whether their chlamydia test result was positive or negative. These data will also be reported.

576 ***Statistical analysis plan***

577 ***Sample size and power calculations***

578 Table 1 summarises the total numbers of randomised clusters required to detect differences in
579 estimated chlamydia prevalence (the primary outcome measure) between intervention and control
580 arms at the end of the trial. The calculations were based on the following assumptions:

- 581 1. The intra-class correlation coefficient (ICC) was estimated from individual practice data to be
582 0.009 [90]. Since combining practices into clusters in the trial design is likely to reduce the ICC,
583 calculations were also performed using ICC = 0.007 and ICC = 0.005.
- 584 2. The design effect (the inflation of the sample size to allow for between area variability) was
585 calculated as $1 + (n - 1) * ICC$, where n is the number of people tested at each area.
- 586 3. All calculations are for 80% power and use a two-sided significance level of 5% [61].

587 Table 1 shows that 54 clusters (27 in each group) are required to detect a difference in chlamydia
588 prevalence between the intervention and control groups of 2% at the end of the trial with 80%
589 power (4% in control and 2% in intervention group). Within each of the geographical areas, 80 men
590 and women aged 16 to 29 years will be tested for chlamydia during each prevalence survey.
591 Statistical power will be increased if a higher than expected chlamydia prevalence is obtained at
592 baseline or if the ICC is lower than estimated. If the ICC is found to be 0.005, 54 clusters will give 89%
593 to detect a difference of 2% at the end of the trial.

594 ***Baseline data***

595 Cluster, clinic and participant baseline characteristics will be summarised by randomised group as

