596 appropriate. There will be no statistical hypothesis tests for this comparison.

597 ***Type of analysis***

598 Primary analyses of the trial endpoint will be according to the intention to treat principle, with
599 clusters analysed according to their randomised group, regardless of the level of uptake of the
600 intervention. Secondary analyses of the measurement outcomes will explore the effect of adherence
601 to the intervention, first by excluding clusters with poor adherence, and second by regression of
602 measures of cluster adherence on outcomes.

603 ***Statistical tests***

604 Formal statistical comparisons will be based on generalised mixed models that can account for
605 cluster, clinic and participant variability. Generalised estimating equation (GEE) approaches, with
606 robust standard errors, will be adopted using STATA statistical software (StataCorp, College Station,
607 TX, USA). Initial analyses will be simple, unadjusted comparisons of randomised areas. If there
608 appear to be any important imbalances between randomised groups in terms of baseline covariates,
609 adjusted analyses will also be performed, and presented in addition to unadjusted comparisons. The
610 impact of other potential confounding factors such as age and gender of the patients and GPs, and
611 socio-economic profile of the area served by the clinic will also be investigated in this analysis. The
612 difference between intervention and control clusters will be estimated, with 95% confidence
613 intervals and p-values from the corresponding hypothesis tests. Statistical significance will be taken
614 as a two-sided p-value less than 0.05, with no adjustment for multiple comparisons.

615 Outcome measures will be assessed as follows:

- 616 • Chlamydia prevalence in clinic attenders after the intervention period will be summarised by
617 randomised group, and by sex and age group. Formal comparisons will be based on
618 hierarchical logistic regression models.
- 619 • Incidence of PID per 100 female patients seen at a clinic will be summarised by randomised
620 group and by age group. Analyses will be based on Poisson regression models.
- 621 • Incidence of epididymitis per 100 male patients seen at a clinic will be summarised by
622 randomised group and by age group. Analyses will be based on Poisson regression models.

- 623 • Testing uptake rates, testing coverage, annual re-testing rates, testing for reinfection and

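### Excluding poorly adherent clusters gives up the randomised comparison, and the adherence regression is worded with adherence as the dependent variable; both are exploratory analyses beneath an intact intention-to-treat primary

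*Protocol*

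**What the plan says.** Under Statistical analysis plan, Type of analysis, the protocol fixes the primary population: "Primary analyses of the trial endpoint will be according to the intention to treat principle, with" "clusters analysed according to their randomised group, regardless of the level of uptake of the" intervention. The same paragraph then turns to adherence, under the label of secondary analyses of the measurement outcomes that explore its effect. There are two steps: "first by excluding clusters with poor adherence, and second by regression of" "measures of cluster adherence on outcomes".

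The paragraph does not define poor adherence or say from which arm clusters may be dropped. Those details may sit in a statistical analysis plan that is not shown, and their absence is not part of this point.

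The package of alerts, recall, feedback, payments and partner-notification resources is described under Intervention. Under Control group: "Control GP clinics and AMSs will be asked to continue diagnosis and management of chlamydia" in their usual way, with a minimal education pack.

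Under Planned subgroup analyses the protocol asks for cautious interpretation. The adherence analyses carry no such statement, and the Statistical tests section sets a two-sided 0.05 threshold without correction for multiplicity.

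**The concern.** Adherence is observed after randomisation and, in substance, only in the arm that has something to adhere to. Removing clusters on that basis leaves self-selected intervention areas facing an unselected control arm. Minimisation on state, baseline prevalence, baseline testing rate and share of young people no longer protects that contrast.

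The protocol itself makes common causes plausible. It plans to study how GP and clinic characteristics relate to both testing uptake and prevalence, and it names area socio-economic profile as a potential confounder.

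The second step has a separate defect. In the usual convention, a regression of A on B has A as the response. Read that way, the outcome predicts adherence, and the coefficient does not answer the stated question, which is what adherence does to the outcome.

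What is at stake is how a null primary result would be read. If uptake is low and the intention-to-treat comparison shows nothing, these are the analyses from which a reader could conclude that the programme works where it is delivered.

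**Working it through.** **The plan's own figure (background).** Sample size and power calculations and Table 1 give 4% v 2%, 80% power, two-sided 5%, ICC 0.009, 80 people per cluster and 54 clusters (27 per arm).
- The continuity-corrected two-proportion formula gives 1239 per arm, 2478 in total, as in Table 1.
- Design effect: 1 + 79 × 0.009 = 1.711.
- 2478 × 1.711 = 4240, and 4240 / 80 = 53.0, rounded up to an even 54. This reproduces. (Table 1 prints 4400 for the inflated total; that does not affect this point.)

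**Step 1, exclusion, with no true effect.** Inputs from the protocol: 27 v 27 clusters of 80, 4% in both arms, ICC 0.009. Inputs that are assumptions: the correlation (rho) between adherence and underlying cluster prevalence, and the number of intervention clusters dropped.

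The size can be seen in closed form:
- Between-cluster SD of true prevalence = √(0.009 × 0.04 × 0.96) = 0.0186, or 1.86 points.
- Dropping the lowest third on a roughly normal adherence score raises the mean score of those kept by 0.364 / 0.667 = 0.545 SD.
- Bias ≈ rho × 0.545 × 1.86 points. At rho = -0.3 this is -0.30; at -0.5 it is -0.51. It is zero at rho = 0 and changes sign with rho.

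A simulation (10,000 runs per setting, beta-distributed cluster prevalence, t-test on cluster proportions) agrees. With 9 of 27 intervention clusters dropped:

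| rho (assumed) | Bias, points | Significant false benefit |
|---|---|---|
| 0 | 0.0 | 2.4% |
| -0.3 | -0.30 | 4.8% |
| -0.5 | -0.51 | 8.0% |
| -0.7 | -0.70 | 12.2% |

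Keeping all clusters gave bias of about 0 and a false-benefit rate of 2.2-2.6%. Over 5 to 13 clusters dropped and rho -0.3 to -0.7, the bias runs from -0.18 to -0.95 points and the false-benefit rate from 3.9% to 16.0%.

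As odds ratios, 3.70% v 4% is (0.0370/0.9630)/(0.04/0.96) = 0.92, and 3.49% v 4% is 0.87. The planned effect is (0.02/0.98)/(0.04/0.96) = 0.49.

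**Step 2, direction of the regression.** In simple linear regression the two slopes multiply to r², and both directions share the test t = r√(n-2)/√(1-r²). A check on 54 simulated points gave slopes 0.276 and 0.324. Their product is 0.089, so r = 0.299 and t = 2.26, with p = 0.0282 in both directions. Reversal changes the meaning of the coefficient, not whether an association is found.

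**Step 2, confounding.** In the same null simulation, regression within the intervention arm gave a significant negative slope in about 2.5% of runs at rho = 0, 15% at -0.3, 37-38% at -0.5 and 66-67% at -0.7. By the equality above, these rates hold whichever variable is the response.

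**The case against.** The strongest reply is that the primary inference is protected. Every cluster is analysed as randomised, and the adherence work is secondary and exploratory. Nothing in the protocol lets it replace a null primary result; the feared claim is a prediction about reporting, not something the document says. That stands, and it limits the weight of the point.

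Other parts also stand. The document does not state that only intervention clusters can be dropped; that is inferred from usual-care controls. The sentence refers to measurement outcomes generally and does not name prevalence. The correlation, its sign and the share dropped have no source in the protocol. The size is modest against the planned effect: with 18 v 27 clusters, the variance of the log odds ratio is about (1.711 / (80 × 0.04 × 0.96)) × (1/18 + 1/27) = 0.052, SE 0.23, so an estimate of 0.87 would carry an interval of roughly 0.56 to 1.36.

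A reader might infer that the reversed regression itself manufactures a benefit. It does not: the test is the same in either direction, and the phrase may be only a slip, given the stated aim. Swapping the variables corrects the estimand and leaves the confounding.

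The reply does not remove the core. Dropping randomised clusters on a post-randomisation variable is decided in this text, and only the threshold is left open. Calling the analysis exploratory does not make the comparison randomised.

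**Conclusion.** The point holds as a cheap improvement, with one plain wording error. Followed as written, step 1 gives a non-randomised comparison and step 2 a coefficient that does not measure the effect of adherence.

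The exclusion bias is nil if adherence is unrelated to underlying prevalence. It favours the intervention by about 0.3 to 0.5 points, with a false-benefit rate of about 5-8%, under assumed correlations of -0.3 to -0.5 and 9 of 27 intervention clusters dropped. It works against the intervention if the correlation is positive. Step 2 is open to the same confounding, in either direction.

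Two stronger inferences are not supported. One is that the trial's main conclusion is compromised: the intention-to-treat analysis is untouched. The other is that these analyses will favour the intervention: the documents give neither the sign nor the size of the correlation.

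**What to change.** 1. Make the main adherence analysis one that keeps all randomised clusters: randomised arm as instrument for the achieved cluster testing rate, final prevalence as outcome, adjusted for baseline prevalence and baseline testing rate. Testing uptake is already collected in both arms, and both baseline measures are already minimisation variables.
2. State its assumption: the arm acts on prevalence through the testing rate. Recall after a positive test and the partner-notification resources may breach this. The test of no effect would still rest on randomisation, but the size of the estimate would have to be read as exploratory.
3. Rewrite step 2 as the outcome regressed on cluster adherence, with the same baseline adjustment, and label it non-randomised.
4. The exclusion analysis need not be deleted. If kept, report it only as a non-randomised sensitivity analysis that cannot support a claim of benefit when intention to treat is null.

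The cost is a few sentences and one extra model using data already planned. The drawbacks are a wider interval and the instrument assumption.
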